4.2. Exclusion Criteria

Subjects meeting any of the following criteria will be excluded from the study:

1. Hypersomnia due to another medical, behavioral, or psychiatric disorder condition (eg, narcolepsy, multiple sclerosis, Parkinson's disease, stroke).
2. Periodic Limb Movement Disorder Sleep Index >15 either on a historical test or during the Screening PSG (if done) causing clinically significant sleep disturbances or impairment of daytime functions that are not better explained by other disorders or medications, as assessed by the investigator.
3. Evidence of untreated or inadequately treated sleep-disordered breathing including:
 - a. Presence of clinically significant and untreated obstructive or central sleep apnea as determined by the Investigator or documented previously
Or documentation of 1 of the following:
 - b. Apnea Index >10 on any historical test (unless a subsequent Apnea Index ≤ 10 was reported after treatment, and the subject agrees to use this treatment throughout the duration of the study) or during the Screening PSG (if done) while on obstructive sleep apnea treatment or untreated
 - c. Clinically significant hypoventilation

Clinical Study Protocol: JZP080-301 Amendment 2

- d. Noncompliance with primary obstructive sleep apnea therapy (compliance defined as positive airway pressure use of ≥ 4 hours per night on $\geq 70\%$ of nights [≥ 5 of 7 nights / week], historical report [with Investigator concurrence] of use of an oral appliance on $\geq 70\%$ of nights [≥ 5 of 7 nights/week], or receipt of an effective surgical intervention for obstructive sleep apnea symptoms)
4. Oxygen saturation level $<95\%$ for at least 5 minutes on room air as measured by pulse oximetry while fully awake during daytime monitoring, or subjects with known or suspected respiratory difficulty, or any condition that may compromise a subject's breathing. If SpO₂ values $<95\%$ are observed at study sites at high geographic elevations and are acceptable to the Investigator, enrollment of the subject requires permission from the Medical Monitor.
5. Succinic semi-aldehyde dehydrogenase deficiency.
6. Uncontrolled hypothyroidism.
7. History of seizures, excluding early childhood nonpathological febrile seizures.
8. History of head trauma associated with loss of consciousness in the past 5 years or history of head trauma more than 5 years prior to screening with ongoing sequelae.
9. Clinically significant parasomnias (e.g., sleep walking, REM sleep behavior disorder, etc.).
10. History or presence of bipolar and related disorders, schizophrenia, schizophrenia spectrum disorders, or other psychotic disorders according to DSM-5 criteria.
11. Current or past (within 1 year) major depressive episode according to DSM-5 criteria. Subjects with depression under control are allowed per the judgment of the Investigator or the treating physician and the antidepressant treatment has to be stable for at least 6 months prior to Screening and remain stable for the duration of the study.
12. Current suicidal risk as determined from history by presence of active suicidal ideation as indicated by positive response to item No.4 or No.5 on the C-SSRS, or any history of suicide attempt.
13. History or presence of any acutely unstable medical condition, behavioral or psychiatric disorder (including active suicidal ideation) that could affect the safety of the subject or interfere with study efficacy, safety assessments, or the ability of the subject to complete the trial per the judgment of the Investigator.
14. Occupation requiring nighttime shift work or variable shift work with early work start times or other occupations that could affect the safety of the subject per the judgment of the Investigator.
15. Usual bedtime later than 1 AM (0100 hours).
16. Female subjects who are pregnant, nursing, or lactating or plan to become pregnant during the study or within 90 days of study completion.
17. Laboratory value(s) outside the laboratory reference range (e.g., aspartate aminotransferase (AST) or alanine aminotransferase (ALT) >3 x upper limits of normal

Clinical Study Protocol: JZP080-301 Amendment 2

[ULN]) or ECG abnormalities considered to be clinically significant that could affect the safety of the subject or interfere with study efficacy, safety assessments, or the ability of the subject to complete the trial per the judgment of the Investigator. (Note: Screening labs and ECG may be repeated once to assess eligibility.)

18. Excessive caffeine use 1 week prior to Baseline or anticipated excessive use defined as >600 mg/day of caffeine leading up to and throughout the Double-blind Randomized Withdrawal Period.
19. Treatment or planned treatment with any CNS sedating agents, including but not limited to benzodiazepines or other sedating anxiolytics, sedating antidepressants, hypnotics, sedatives, neuroleptics, opioids, barbiturates, phenytoin, ethosuximide, medications containing valproic acid or its sodium salt (e.g., depakene and DepakoteTM), or other sedating antiseizure medications, melatonin, muscle relaxants, general anesthetics, or any other medication in which the subject experiences sedation are prohibited during the study.. Treatment must have been discontinued at least 2 weeks or 5 half-lives prior to enrollment (whichever is longer). (Discontinuation for the purpose of study enrollment is permitted only if considered safe and medically appropriate by the Investigator, and approved by the Medical Monitor.) The Investigator must ensure that discontinuation from these medications is medically supervised. Subjects must abstain from these medications during the study.
20. Treatment or planned treatment with stimulants or alerting agents in subjects who have not been on a stable dose of these medications, including but not limited to pseudoephedrine, methylphenidate, amphetamines, modafinil and armodafinil. Treatment must have been discontinued at least 2 weeks or 5 half-lives prior to enrollment (whichever is longer). Discontinuation for the purpose of this study is permitted only if considered safe and medically appropriate by the investigator, and approval from the Medical Monitor. The Investigator must ensure that discontinuation from these medications is medically supervised. Subjects who have not been on a stable dose of stimulants or alerting agents when entering the study must abstain from these medications during the study.
21. A positive breath alcohol test or urine drug screen for benzodiazepines or other drugs of abuse, except for a prescribed medication allowed by the protocol. A positive urine drug screen for cannabinoids whether prescribed or not. If the interpretation of positive results is ambiguous, or there are extenuating circumstances, a repeat breath alcohol test or urine drug screen may be performed if approved by the Investigator and the Medical Monitor.
22. Current or past substance use disorder (including alcohol) according to DSM-5 criteria or the subject is unwilling to refrain from consuming alcohol, cannabinoids, or prohibited medications during the study.
23. Received an investigational drug in the past 30 days or 5 half-lives (whichever is longer) prior to the Screening Visit, or plans to use an investigational drug (other than the study drug) during the study.
24. Previously participated in a clinical trial of JZP-258.

Clinical Study Protocol: JZP080-301 Amendment 2

25. Nicotine dependence that has an effect on sleep (eg, a subject who routinely awakens at night to smoke).
26. Allergy or sensitivity to malic acid, sucralose or any ingredients in the study drug formulation or placebo.

4.3. Screening and Randomization Eligibility

4.3.1. Screening Eligibility

Subjects will be considered eligible to enroll if they meet the inclusion criteria and do not meet any exclusion criteria. Subjects who do not meet eligibility criteria at the Screening Visit or the Baseline Visit will be considered screen failures.

4.3.2. Rescreening (30 days)

Subjects may be allowed to rescreen (1 time) if they previously did not meet all eligibility requirements at Screening and the Baseline Visit. Rescreening may only occur following resolution of transient exclusionary conditions or stabilization of conditions that were exclusionary and reversible (eg, unstable hypothyroidism, electrolyte abnormalities) and with the approval of the Medical Monitor. Subjects who are approved for rescreening must be reconsented and all screening procedures must be repeated.

4.3.3. Randomization Eligibility

Subjects are eligible to be randomized into the Double-blind Randomized Withdrawal Period if the following conditions are met at the End of Stable Dose Visit:

- The dose and regimen of JZP-258 remains unchanged during the Stable Dose Period, and subjects demonstrate adequate compliance with dosing.
- No ongoing AEs occur due to JZP-258 treatment that would require dose adjustment or treatment discontinuation during the Double-blind Randomized Withdrawal Period.
- Subjects who are on Xyrem at study entry must have PGIC scale ratings at the end of the Stable Dose Period of no change, minimal, much, or very much improved compared with the Baseline Visit.
- Subjects who are not on Xyrem at study entry must have PGIC scale ratings of minimal, much, or very much improved compared with the Baseline Visit and a lower ESS score at the end of the Stable Dose Period compared with the Baseline Visit.

4.3.4. Contraception Requirements

Women of childbearing potential (WOCBP) are required to use highly effective contraceptive measures, defined as methods that can achieve a failure rate of less than 1% per year when used consistently and correctly.

The following contraceptive methods are considered highly effective:

Combined (estrogen and progestogen containing) hormonal contraception associated with inhibition of ovulation: oral, intravaginal, transdermal; progestogen-only hormonal contraception

Clinical Study Protocol: JZP080-301 Amendment 2

associated with inhibition of ovulation: oral, injectable, implantable; intrauterine device, intrauterine hormone releasing system, bilateral tubal occlusion, vasectomized partner, sexual abstinence.

Male subjects who have not had a vasectomy and who are sexually active with a female partner of childbearing potential must agree to use condoms with their partners from Day 1 through 30 days after the last dose of study treatment.

Note: A woman is considered of childbearing potential (ie, fertile) following menarche until becoming postmenopausal unless permanently sterile.

5. STUDY TREATMENT(S)

5.1. Description of Study Drug

Study Drug: JZP-258 mixed oxybate salts oral solution, 0.5 g/mL

Placebo (for Double-blind Randomized Withdrawal Period only): A matching oral solution to JZP-258 will be provided. The placebo formulation is an aqueous solution consisting of sodium citrate, malic acid, and sucralose. All ingredients are compendial (USP/NF).

5.2. Treatments Administered

During the Open-label Treatment Titration and Optimization Period, all subjects will receive open-label JZP-258.

During the Stable Dose Period, all subjects will receive open-label JZP-258 at the same unchanged dose that they received at the end of the Open-label Treatment Titration and Optimization Period.

During the Double-blind Randomized Withdrawal Period, all subjects will receive blinded study drug. At the end of the Stable Dose Period, subjects will enter the Double-blind Randomized Withdrawal Period and will be randomized 1:1 to receive either JZP-258 (at the dose taken at the end of the Stable Dose Period) or Placebo (at a volume and regimen equivalent to the JZP-258 dose taken at the end of the Stable Dose Period). If the optional IA is conducted and the predefined efficacy stopping rule is met, per DMC communication enrollment and randomization to placebo may be stopped. All subjects who have not already been randomized would then receive open-label JZP-258 during the Double-blind Randomized Withdrawal Period. All subjects who have already entered the Double-blind Randomized Withdrawal Period will complete that period as planned.

During the Open-label Safety Extension Period all subjects will receive open-label JZP-258.

During the PK study, all enrolled subjects will receive open-label JZP-258 with no change in dose required.

Study drug will be dispensed at clinic visits and, if applicable, at intervals specified by state or local regulations or to resolve logistical issues.

5.3. Treatment Initiation, Titration, and Optimization

During the Open-label Treatment Titration and Optimization Period subjects will either transition from Xyrem to JZP-258, or initiate treatment with JZP-258, based on treatment status at study entry:

1. Subjects who are on a stable dose of Xyrem at study entry will switch from Xyrem to the same dosing regimen of JZP-258. The dosing regimen of JZP-258 then may be adjusted until an optimally effective and tolerable dosing regimen is established.

Subjects who are not on Xyrem at study entry will initiate JZP-258 either as a once nightly or twice nightly dosing regimen at the discretion of the investigator (see [Section 3.3](#)). The dosing

Clinical Study Protocol: JZP080-301 Amendment 2

regimen of JZP-258 may be adjusted until an optimally effective and tolerable dosing regimen is established.

The aim of JZP-258 dose titration and optimization is to maximize efficacy (reduction in IH symptoms, e.g., EDS, sleep inertia, and long sleep duration) while ensuring adequate nocturnal sleep and minimizing risk associated with safety and tolerability. The Medical Monitor should be contacted with any questions related to dosing and titration.

5.3.1. Subjects Starting Once Nightly Dosing Regimen

Subjects who report difficulty awakening as a result of significant sleep inertia or long sleep time (>11 hours/24 hours) may be considered for a once nightly dosing regimen at the discretion of the investigator.

For subjects who initiate dosing JZP-258 as a once nightly dosing regimen, the starting dose should not exceed 3 g, the maximal single dose should not exceed 6 g, and the maximum nightly dose should not exceed 9 g. Titration should proceed at a rate of ≤ 1.5 g/night per week with incremental increases every few days as tolerated. The dose should be taken at bedtime. If a subject develops treatment associated sleep inadequacy on a single nightly dose, the dose may be taken after an initial period of sleep.

Subjects who initiate JZP-258 as a once nightly dosing regimen may switch to a twice nightly dosing regimen to optimize efficacy and tolerability, or to ensure adequate sleep duration. When switching to the twice nightly dosing regimen, the total nightly dose should be the same or no more than 1.5 g higher than the current dose. The first dose will be administered at bedtime or after an initial period of sleep and the second dose should be administered 2.5 to 4 hours later. Titration should proceed at a rate of ≤ 1.5 g/night per week, as required for optimal efficacy and tolerability; the increase in dose can be made incrementally as tolerated. The total nightly dose should not exceed 9 g/night. The maximal single dose should not exceed 6 g/night. The dose may be reduced at any time, as needed, for tolerability.

5.3.2. Subjects Starting Twice Nightly Dosing Regimen

Subjects who report disrupted nighttime sleep or difficulty maintaining sleep may be considered for a twice nightly dosing regimen at the discretion of the investigator.

For subjects who initiate JZP-258 as a twice nightly dosing regimen, the starting dose should not exceed 4.5 g/night divided into 2 doses (2.25 g each). The first dose will be administered at bedtime or after an initial period of sleep; the second dose should be administered 2.5 to 4 hours later. Titration should proceed at a rate of ≤ 1.5 g/night per week, as required for optimal efficacy and tolerability; the increase in dose can be made incrementally as tolerated. The maximal single dose should not exceed 6 g, and the total nightly dose should not exceed 9 g. The dose may be reduced at any time, as needed, for tolerability. If the subject does not achieve adequate sleep duration, the first dose may be taken after an initial period of sleep.

Subjects who initiate JZP-258 as a twice nightly dosing regimen may switch to once nightly if they are unable to wake up to take the second dose, or have difficulty awakening from sleep in the morning. The same first dose taken in the twice nightly dose regimen may be the starting

Clinical Study Protocol: JZP080-301 Amendment 2

dose when switching to once nightly dosing regimen. Titration should then proceed at a rate of ≤ 1.5 g/night per week. The maximal once nightly dose may not exceed 6 g.

While most subjects should be able to achieve an efficacious and tolerable dose while maintaining adequate sleep duration with a twice-nightly dosing regimen, in some instances there may be subjects who still are not maintaining adequate sleep duration. In these instances, subjects may divide their nightly dose into 3 administrations to ensure adequate sleep duration. In these cases, the same dosing intervals (2.5 to 4 hours), titration schedule (≤ 1.5 g/night per week) and total nightly dose (9 g) remain applicable (See Table 2).

Table 2 JZP-258 Dosing Recommendations

Dosing Regimen	Starting Nightly Dose	Titration Increments ^a	Maximum Nightly Dose
Once Nightly	≤ 3 g	≤ 1.5 g/night per week	6 g ^b
Twice Nightly	≤ 4.5 g (divided)	≤ 1.5 g/night per week	9 g
Thrice Nightly (titration only, not a starting dose)	Not applicable	≤ 1.5 g/night per week	9 g

NOTE: the aim of JZP-258 dose titration and optimization is to maximize efficacy (reduced IH symptoms, e.g.. EDS, sleep inertia, and sleep duration) while ensuring adequate nocturnal sleep and minimizing risks associated with safety and tolerability.

^a The weekly increase in dose of ≤ 1.5 g/night may be made incrementally every few days as tolerated.

^b The maximum single dose should not exceed 6 g and the maximum nightly dose should not exceed 9 g at twice or thrice nightly dosing

EDS= excessive daytime sleepiness; IH=idiopathic hypersomnia

Subjects will be instructed to take each dose while in bed and remain in bed after each dose. Subjects will also be instructed to complete a daily dosing diary (Section 6.7). For all dosing regimens, investigators should caution subjects about operating hazardous machinery, including automobiles or airplanes until subjects are reasonably certain that the study drug does not affect them adversely (eg, impair judgment, thinking or motor skill).

5.4. Method of Assigning Subjects to Treatment Groups

At the end of the Stable Dose Period, subjects meeting randomization criteria will be randomized 1:1 to either JZP-258 at the stable dose established in the previous 2 weeks or to Placebo at a volume equivalent to the JZP-258 dose that was established in the previous 2 weeks.

Randomization will be stratified by the subject's use of stimulant agent and/or Xyrem at baseline per the following baseline medication group: 1) subjects on Xyrem only; 2) subjects on Xyrem and an additional stimulant or alerting agent; 3) subjects not currently taking Xyrem but are taking a stimulant or alerting agent; or 4) subjects not currently taking Xyrem or a stimulant or alerting agent.

Clinical Study Protocol: JZP080-301 Amendment 2

At the time of the IA, if the predefined efficacy stopping rule is met, per DMC communication, enrollment and randomization to placebo treatment may stop. All subjects who have not already been randomized would then enter the Double-blind Randomized Withdrawal Period on open-label JZP-258. All subjects who have already entered the Double-blind Randomized Withdrawal Period will complete that period as planned. The IA is optional and will be performed based on enrollment.

During the open-label periods (Open-label Treatment Titration and Optimization Period, Stable Dose Period, and Open-label Safety Extension Period) all subjects will receive open-label JZP-258.

5.5. Randomization and Blinding

A statistician selected by Jazz Pharmaceuticals will prepare and retain the master randomization code for the entire study. This statistician will not be involved in the analysis of this study. The randomization codes will be generated and retained according to Jazz Pharmaceuticals Standard Operating Procedure on the generation, distribution, and access to randomization information for clinical studies. Unless there is an emergency that requires the release of the subject's assigned treatment, or it is required for regulatory reporting, the code will not be broken or released until all study data are collected and accepted for analysis (see [Section 6.15.9](#) and [Section 6.15.10](#)).

The Investigator will access an IWRS to randomize subjects.

During the Open-label Treatment Titration and Optimization Period, Stable Dose Period, and Open-label Safety Extension Period of this study, the dose of study drug will not be blinded to the subjects or the study personnel. A double-blind approach will be used during the Double-blind Randomized Withdrawal Period. JZP-258 and JZP-258 placebo oral solution will be matched in volume, to ensure adequate blinding of the subject and study personnel.

The IA is optional. If conducted, it will be performed by an unblinded statistician not directly involved with the conduct and analysis of the study. Details of study team blinding as well as maintaining blind for the planned IA will be detailed in a separate document and as applicable, in the DMC charter. All data analysis output by treatment group reviewed at the closed session of the DMC meeting will be held in confidence by the DMC members, and study team members will remain blinded until the data extraction for final efficacy analysis is performed. A Jazz team comprised of individuals independent of the study team may be made aware of the interim data to assess DMC communications; however, interim data will not be shared outside of this independent team until treatment unblinding.

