5.5. Randomization and Blinding

An Interactive Web Recognition System (IWRS) vendor will prepare and retain the master randomization code for the entire study. The IWRS vendor will not be involved in the analysis of this study.

At the end of the SDP, subjects meeting randomization criteria will be randomized via IWRS 1:1 to either JZP-258 at the stable dose established in the previous 2 weeks or to Placebo at a volume equivalent to the JZP-258 dose that was established in the previous 2 weeks. Randomization will be stratified by the subject's use of stimulant agent and / or Xyrem at baseline per the following baseline medication group:

Group 1: subjects on Xyrem only

Group 2: subjects on Xyrem and an additional stimulant or alerting agent

Group 3: subjects not currently taking Xyrem but are taking a stimulant or alerting agent

Group 4: subjects not currently taking Xyrem or a stimulant or alerting agent.

A double-blind approach will be used during the DBRW. JZP-258 and JZP-258 placebo oral solution will be matched in volume, to ensure adequate blinding of the subject and study personnel. The Jazz study team, with the exception of the Jazz clinical trial material supply group will remain blinded until the formal database snapshot for the final comparative efficacy analysis.

During the DBRW a subject's treatment assignment should only be unblinded when knowledge of the treatment is necessary for immediate medical management of the subject. In the case of an immediate medical emergency, an Investigator or his / her designee will be able to unblind a subject at any time via the IWRS without any obligation to contact the Medical Monitor prior to emergency unblinding. The Investigator or his/her designee is responsible for all decisions

related to medical treatment in the study. A comment must be entered in the source documentation to specify the reason for unblinding, along with the date on which the code was broken and the identity of the person authorizing the unblinding. Subjects for whom the blind is broken will be withdrawn from the study. The Medical Monitor should be notified of the unblinding as soon as possible, but the results of the unblinding should not be disclosed to the Medical Monitor.

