5.6. Timing of analyses

The final comparative efficacy analysis for this study will occur after all randomized subjects complete or discontinues the DBRW period. For these analyses, a formal database snapshot including data per a cut-off date is planned, which will occur after the last randomized subject completes or discontinues the DBRW period. Unblinding will occur after the data extraction is completed. This analysis will include results on the final comparative analyses of efficacy end points and all available safety, open-label efficacy, and pharmacokinetic data. These results will be summarized in an interim CSR.

A final analysis will occur after all subjects complete or discontinue from the study. These analyses will be based on a locked database and will include final summaries across the study on safety, open-label efficacy, and pharmacokinetic results. Results will be summarized in a final CSR.

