10.2.1. Adverse Events of Special Interest

TEAEs of special interest will be summarized and may include the terms or categories noted below. The list of PTs of special interest will be reviewed and finalized prior to each database extraction for analyses specified in section 5.6.

- Anxiety
- Confusion
- Convulsions
- Depressed consciousness
- Depression and suicidality
- Psychotic and dissociative disorders
- Impaired attention or cognitions
- Parasomnias
- Respiratory failure and respiratory depression
- Drug Abuse
- Accidents and Injuries

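### Protocol 5.5 gives two code-release rules that disagree, and under the one the SAP follows the special-interest adverse event list is finalized a second time with the arms known

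*Protocol*

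**What the plan says.** **When the code is released**
- Protocol 5.5, first paragraph: apart from emergencies and regulatory reporting, "the code will not be broken or released until all study data are collected and accepted for analysis".
- Protocol 5.5, last paragraph, written around the optional interim analysis: "study team members will remain blinded until the data extraction for final efficacy analysis is performed".
- SAP 5.5: the sponsor's study team, other than the clinical supply group, "will remain blinded until the formal database snapshot for the final comparative efficacy analysis".
- SAP 5.6: that snapshot is one "which will occur after the last randomized subject completes or discontinues the DBRW period", and "Unblinding will occur after the data extraction is completed". The results go into an interim study report.
- SAP 5.6, second stage: "A final analysis will occur after all subjects complete or discontinue from the study". It uses a locked database and gives "final summaries across the study on safety, open-label efficacy, and pharmacokinetic results".
- SAP 7.6 lists three changes from the protocol. The unblinding point is not one of them.

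**How special-interest events are defined**
- SAP 10.2.1 names eleven categories in permissive terms and lists no preferred terms (PTs). It then says: "The list of PTs of special interest will be reviewed and finalized prior to each database extraction for analyses specified in section 5.6".
- SAP 10.2 produces every treatment-emergent adverse event (TEAE) summary in two versions, one across the study and one for the DBRW by randomized arm. The special-interest summary is among them.

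**The concern.** The two sentences in Protocol 5.5 give sites, ethics committees and the sponsor different answers on when the arms become known. The SAP has in effect chosen one of them without saying so.

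The choice matters because of SAP 10.2.1. If the code stayed sealed to the end of the study, finalizing the list before each extraction would be harmless, since both finalizations would be blinded. Under the SAP's timing only the first is. At the second, those deciding which PTs count as special interest can know how each PT splits between JZP-258 and placebo.

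Placebo is given only in the DBRW, so this is the trial's only placebo-controlled safety comparison. What goes into a by-arm grouping in that period should be settled before the arms are known.

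**Working it through.** The plan states no figure on this point, so the check is mainly one of sequence.

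**1. Can the two sentences of Protocol 5.5 both hold?** A study team unblinded at the final efficacy extraction requires a released code. Protocol 9.9.2 places the final efficacy analyses at the end of the DBRW, and Protocol 9.9.5 places the final safety analyses at the end of the study. At the first of these, extension and follow-up data are still being collected, so the first sentence is not yet satisfied. The two agree only if all study data is read as meaning the data for the comparative analysis, and the text does not say that.

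**2. Order of events under the SAP**
1. The last randomized subject leaves the DBRW.
2. The PT list is finalized for the first time (SAP 10.2.1), blinded.
3. The snapshot is extracted (SAP 5.6).
4. Unblinding, then the interim report.
5. The extension and follow-up run to completion.
6. The PT list is finalized for the second time, with the arms known.
7. Database lock, then the final report.

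That is two finalizations, one blinded and one not.

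**3. Length of the gap.** Period lengths are from Protocol 3.1. As a check, treatment time is 10 + 2 + 2 + 24 = 38 weeks to 14 + 2 + 2 + 24 = 42 weeks, which matches the 38 to 42 weeks in Protocol 3.4. After the DBRW the last randomized subject has 24 (extension) + 2 (follow-up) = 26 scheduled weeks left. Time spent on cleaning and extraction before unblinding shortens this.

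**4. What depends on the list.** In SAP 10.2 only the special-interest table and its matching listing use it. The TEAE definition, the attribution of events to periods, the coding dictionary version, and the tables by system organ class and PT, by severity, by relatedness and by withdrawal do not. Efficacy does not.

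**5. Does the second list reach the DBRW table?** This is not stated outright, but it is a fair inference:
- SAP 5.6 and Protocol 9.9.5 both put final safety summaries at the end of the study.
- SAP 10.2 includes a DBRW by-arm version of each TEAE summary and exempts none.
- For a subject who does not enter the extension, the DBRW event window in SAP 10.2 runs to 30 days after the last dose. The snapshot waits only for the last subject to leave the DBRW, so some DBRW events can arrive after it and the table would then need updating.

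No sentence freezes the DBRW list at the first extraction or requires blinded reviewers for the second.

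**The case against.** The strongest reply is that staged analysis is already in the protocol. Sections 9.9.2 and 9.9.5 separate final efficacy from final safety, and the last paragraph of 5.5 ends team blinding at the efficacy extraction, so the SAP only carries this out. **That stands.** A reader might infer a plain conflict between protocol and SAP. The documents show instead an inconsistency inside Protocol 5.5, with the SAP following one of its two rules.

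It can also be said that the categories are named in advance, that the first list is finalized blinded and reported in the interim report so a later change could be traced, that PT-level DBRW tables would show what had been regrouped, and that a second review has an ordinary purpose because a 24-week extension can bring new PTs. SAP 7.4 plans no inference on safety data. **All of this stands and limits the consequence.** It does not close the gap, because the category wording is permissive and no PTs are fixed. SAP section 3 requires departures from the plan to be reported with reasons and unplanned post hoc analyses to be identified. But a second finalization is itself a planned step, so a revised list would not clearly trigger either requirement.

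Three stronger readings are tempting and are not supported:
- **All by-arm DBRW safety results can be redefined.** Only the special-interest grouping can.
- **DBRW records can be edited or recoded once the arms are known.** The SAP does distinguish a snapshot from a lock, but nothing permits unblinded recoding. Data handling is left to a data management plan and procedures (Protocol 10.1) that are not among these documents. Whether the records are frozen at the snapshot is unknown, not shown to be absent.
- **Sites receive subject-level assignments at unblinding.** No text says so. The SAP 5.5 sentence concerns the sponsor's study team.

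**Conclusion.** The point holds in a limited form. Protocol 5.5 needs one code-release rule. Under the rule the SAP uses, one descriptive DBRW by-arm grouping can be redefined with the arms known.

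The 26 weeks measure elapsed time, not bias. The documents give no special-interest event counts or rates, so no effect in percentage points can be derived. The primary and key secondary endpoints and the type 1 error rate are untouched.

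The conclusion rests on three assumptions: unblinding follows the first extraction without long delay; the final report repeats the DBRW by-arm special-interest table, which is inferred; and those finalizing the second list have access to the assignments, which the SAP does not rule out. The consequence is small, but this is the only placebo-controlled safety comparison and the correction costs almost nothing.

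**What to change.** 1. **Protocol 5.5 and SAP 7.6.** Replace the two sentences in Protocol 5.5 with a single staged rule that names the unblinding point, consistent with SAP 5.5 and 5.6. Record it in SAP 7.6.
2. **SAP 10.2.1.** State that the PT list finalized before the first, blinded extraction governs all DBRW by-arm special-interest tables in both the interim and final reports. PTs added before the second extraction are used only in the across-study tables, or are labelled post hoc if shown by arm. This keeps the second review for new extension events.

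The cost is a few sentences of protocol and SAP text. No data collection, sample size or efficacy analysis changes.
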